2.5.2 Group B

An interim efficacy analysis to conclude early that the estimated single-arm SPR proportion at 4 weeks after the vaccination series exceeds the null proportion (55%) will not be conducted. Early stopping due to concerns about poor vaccine responses may occur. If the study enrollment allows interim analysis on the SPR proportion to be useful to affect the conduct of the study, a two-sided 99.9% confidence interval may be provided with the proportion estimate. The interval upper bound below 45% (10% lower than the null proportion) may be used as guidance.

3 Outcome Measures

3.1 Primary Outcome Measures

3.1.1 Group A

- [For Primary Objectives 1 and 2] SPR defined as HBsAb ≥10 mIU/mL at 8 weeks after the two-dose series (at Week 12) in Arm 1 and at 4 weeks after the three-dose series (at Week 28) in Arms 2 and 3
- 2. [For Primary Objective 3] Reported AEs from study vaccination initiation to study discontinuation

3.1.2 Group B

- 1. [For Primary Objective 1] SPR defined as HBsAb ≥10 mIU/mL at 4 weeks after the vaccination series (Week 28)
- 2. [For Primary Objective 2] Reported AEs from study vaccination initiation to study discontinuation

3.2 Secondary Outcome Measures

3.2.1 Group A

- 1. HBsAb titer at the following study visits in Arm 1:
 - a. Week 4 [Secondary Objective 6]
 - b. Week 8 [Secondary Objectives 3, 5, and 6]
 - c. Week 12 [Secondary Objectives 1, 3, 5, and 6]
 - d. Week 24 [Secondary Objective 6]
 - e. Week 28 [Secondary Objectives 3 and 5]
 - f. Week 52 [Secondary Objectives 3 and 5]
 - g. Week 72 [Secondary Objective 9]
- 2. SPR defined as HBsAb ≥10 mIU/mL at the following study visits in Arm 1:
 - a. Week 4 [Secondary Objective 6]
 - b. Week 8 [Secondary Objectives 3, 5, and 6]
 - c. Week 12 [Secondary Objectives 3, 5, and 6]
 - d. Week 24 [Secondary Objective 6]
 - e. Week 28 [Secondary Objectives 3 and 5]
 - f. Week 52 [Secondary Objectives 3 and 5]
 - g. Week 72 [Secondary Objective 9]
- 3. HBsAb titer at the following study visits in Arm 2:
 - a. Week 4 [Secondary Objective 6]
 - b. Week 8 [Secondary Objective 6]
 - c. Week 12 [Secondary Objective 6]
 - d. Week 24 [Secondary Objective 6]
 - e. Week 28 [Secondary Objectives 2 and 5]
 - f. Week 32 [Secondary Objectives 4 and 5]
 - g. Week 48 [Secondary Objectives 4 and 5]
 - h. Week 72 [Secondary Objectives 4, 5, and 9]
- 4. SPR defined as HBsAb ≥10 mIU/mL at the following study visits in Arm 2:
 - a. Week 4 [Secondary Objective 6]
 - b. Week 8 [Secondary Objective 6]
 - c. Week 12 [Secondary Objective 6]
 - d. Week 24 [Secondary Objective 6]
 - e. Week 28 [Secondary Objective 5]
 - f. Week 32 [Secondary Objectives 4 and 5]
 - g. Week 48 [Secondary Objectives 4 and 5]
 - h. Week 72 [Secondary Objectives 4, 5, and 9]
- 5. HBsAb titer at the following study visits in Arm 3:
 - a. Week 4 [Secondary Objective 6]
 - b. Week 8 [Secondary Objective 6]

- c. Week 12 [Secondary Objective 6]
- d. Week 24 [Secondary Objective 6]
- e. Week 28 [Secondary Objectives 1, 2 and 3]
- f. Week 32 [Secondary Objectives 3 and 4]
- g. Week 48 [Secondary Objectives 3 and 4]
- h. Week 72 [Secondary Objectives 3 and 4]
- 6. SPR defined as HBsAb ≥10 mIU/mL at the following study visits in Arm 3:
 - a. Week 8 [Secondary Objective 6]
 - b. Week 12 [Secondary Objective 6]
 - c. Week 24 [Secondary Objective 6]
 - d. Week 28 [Secondary Objective 3]
 - e. Week 32 [Secondary Objectives 3 and 4]
 - f. Week 48 [Secondary Objectives 3 and 4]
 - g. Week 72 [Secondary Objectives 3 and 4]
- 7. Grade ≥2 AEs within 4 weeks after each injection [Secondary Objective 7]

3.2.2 Group B

- 1. HBsAb titer at the following study visits:
 - a. Weeks 4, 8, 12, and 24 [Secondary Objective 3]
 - b. Week 28 [Secondary Objective 1]
 - c. Weeks 32, 48, and 72 [Secondary Objective 2]
- 2. SPR defined as HBsAb ≥10 mIU/mL at the following study visits:
 - a. Weeks 4, 8, 12, and 24 [Secondary Objective 3]
 - b. Weeks 32, 48, and 72 [Secondary Objective 2]
- 3. Grade ≥2 AEs within 4 weeks after each injection [Secondary Objective 4]

4 Estimands and Estimation

* The strategies for handling intercurrent events (e.g. treatment policy strategy, principal stratum strategy, composite variable strategy) are as described in ICH E9(R1) Addendum on Estimands and Sensitivity Analysis in Clinical Trials.

4.1 Primary Efficacy Estimands

4.1.1 Primary Objective 1 from Section 2.3.1 for Group A

Estimand Description	Difference in the probabilities of SPR (HBsAb titer ≥10 mIU/mL) between 2-dose regimen of HEPLISAV-B and 3-dose regimen of ENGERIX-B in HBV vaccine-experienced adults living with HIV-1 who failed to achieve a protective level of antibodies against HBsAg.
Treatment	2-dose regimen of HEPLISAV-B vs. 3-dose regimen of ENGERIX-B
Target Population	HBV vaccine-experienced adults living with HIV-1 and on ART who failed to achieve a protective level of antibodies against HBsAg, have suppressed HIV-1 RNA and CD4+ T-cell count ≥100 cells/mm³, and initiate vaccination series.

Variable	SPR at 12 weeks after the initiation of the HEPLISAV-B vaccine series, or SPR at 28 weeks after the initiation of the ENGERIX- vaccine series.
Handling of Intercurrent Events	 Incomplete or delayed vaccine series: Participants with incomplete or delayed vaccine series are included. (Treatment Policy Strategy*) Pregnancy: Participants who become pregnant on study have the option of completing the vaccination series and the study. (Principal Stratum Strategy*) Death: Participants who die prior to completion of vaccine series are included. (Treatment Policy Strategy*).
Population-Level Summary	Difference in proportions.

4.1.2 Primary Objective 2 from Section 2.3.1 for Group A

Estimand Description	Difference in the probabilities of SPR (HBsAb titer ≥10 mIU/mL) between 3-dose regimen of HEPLISAV-B and 3-dose regimen of ENGERIX-B in HBV vaccine-experienced adults living with HIV-1 who failed to achieve a protective level of antibodies against HBsAg.
Treatment	3-dose regimen of HEPLISAV-B vs. 3-dose regimen of ENGERIX-B
Target Population	HBV vaccine-experienced adults living with HIV-1 and on ART who failed to achieve a protective level of antibodies against HBsAg, have suppressed HIV-1 RNA and CD4+ T-cell count ≥100 cells/mm3, and initiate vaccination series.
Variable	SPR at 28 weeks after the initiation of the vaccine series.
Handling of Intercurrent Events	 Incomplete or delayed vaccine series: Participants with incomplete or delayed vaccine series are included. (Treatment Policy Strategy*) Pregnancy: Participants who become pregnant on study have the option of completing the vaccination series and the study. (Principal Stratum Strategy*) Death: Participants who die prior to completion of vaccine series are included. (Treatment Policy Strategy*)
Population-Level Summary	Difference in proportions.

4.1.3 Primary Objective 1 from Section 2.3.1 for Group B

Estimand	Probability of SPR (HBsAb titer ≥10 mIU/mL) after HEPLISAV-B vaccination in adults living with HIV-1 without known history of HBV vaccination.
Description Treatment	3-dose regimen of HEPLISAV-B
Target Population	Adults living with HIV-1 and on ART without known history of HBV vaccination who have suppressed HIV-1 RNA and CD4+ T-cell count ≥100
	cells/mm³, and initiate vaccination series.
Variable	SPR at 28 weeks after the initiation of the vaccine series.

Handling of	1. Incomplete or delayed vaccine series: Participants with incomplete or
Intercurrent	delayed vaccine series are included. (Treatment Policy Strategy*)
Events	2. Pregnancy: Participants who become pregnant on study have the option
	of completing the vaccination series and the study. (Principal Stratum
	Strategy*)
	3. Death: Participants who die prior to completion of vaccine series are
	included. (Treatment Policy Strategy*)
Population-Level	Proportion.
Summary	

4.2 Primary Efficacy Estimation

4.2.1 Analysis Sets for 4.1.1 - 4.1.3

All participants who have met the study eligibility criteria according to the latest protocol and received any study vaccination will be included in each analysis.

4.2.2 Details on Outcome Measures for 4.1.1 - 4.1.3

- SPR at 12 weeks after the study randomization/registration for the 2-dose HEPLISAV-B vaccine series will be determined by antibody result at Week 12 study visit using the visit window specified in the protocol schedule of events. If the completion of vaccine series is delayed up to 4 weeks (as described in Protocol Version 2.0 Section 6.2.3 on Missed Vaccination Visits), then the subsequent antibody result within 8 weeks with an analogous visit window will be used.
- SPR at 28 weeks after the initiation of the 3-dose vaccine series (HEPLISAV-B or ENGERIX-B) will be determined by antibody result at Week 28 study visit using the visit window specified in the protocol schedule of events. If the completion of vaccine series is delayed up to 4 weeks (as described in Protocol Version 2.0 Section 6.2.3 on Missed Vaccination Visits), then the subsequent antibody result within 4 weeks with an analogous visit window will be used.

4.2.3 Handling of Missing Data for 4.1.1 - 4.1.3

Each analysis on SPR will be conducted on participants with available data, under the assumption of missing completely at random (Li, Wang, Liu, Chan, 2011).

A sensitivity analysis will be conducted with the following imputations.

- Missing SPR will be imputed if both antibody results immediately prior to and after the
 missed visit are <10 mIU/mL, or if both are ≥10 mIU/mL. This is assuming that there is no
 change in the response between the visits where data are available.
- If after the above imputation, the total missing SPR results is >10% (above what was accounted for in the study design), then the following additional imputation will be made in the sensitivity analysis:
 - For the recipients assigned to 3-dose vaccine series, the antibody result from the subsequent visit that occurs within 4 weeks of the missed SPR visit will be used to allow the result from Week 32 study visit, accounting for the visit window.

For the recipients assigned to 2-dose vaccine series, the antibody result from a visit within 4 weeks of the missed SPR visit (8 weeks after the vaccine series) will be used to allow the result from Week 8 study visit (4 weeks after the vaccine series) or from an unscheduled visit that occurs subsequent to the missed visit within 4 weeks. The visit window from the protocol schedule of evaluations will be applied.

The number of imputations in the sensitivity analysis will be summarized by study arm.

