2.1.1 Group A (Non-responders, N=561)

The study is designed as an open-label three-arm study, where participants are randomized in 1:1:1 ratio to the following study arms, stratified by sex at birth (male vs. female) and diabetes diagnosis status (yes vs. no).

- Arm 1: Two doses of HEPLISAV-B at weeks 0 and 4
- Arm 2: Three doses of HEPLISAV-B at weeks 0, 4, and 24
- Arm 3: Three doses of ENGERIX-B at weeks 0, 4, and 24

Randomization will use permuted blocks and balancing by main site.

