2.4 Overview of Sample Size Considerations

2.4.1 Group A

A two-sided type I error rate is targeted at the pre-specified overall alpha level of 5% for the two primary analysis comparisons in Group A. To preserve the overall type I error rate in Group A and to allow flexible interim monitoring, a Bonferroni correction is applied, and a two-sided type I error rate of 2.5% each for the non-inferiority comparison between Arm 1 and Arm 3 and for the superiority comparison between Arm 2 and Arm 3 is allocated.

The sample size of N=187 per arm was derived as follows.

1. Non-inferiority comparison between Arms 1 and 3: For the primary objective to show that SPR proportion in Arm 1 is non-inferior to the SPR proportion in Arm 3 within the non-inferiority margin of 10%, we assume that 70% in the control arm (Arm 3) will achieve SPR. We assume the proportion of participants achieving SPR with two doses of HEPLISAV-B (Arm 1) will be higher at 75%. As a non-inferiority design, this comparison is powered to show that the SPR proportion in Arm 1 is not lower than that of Arm 3 (control) by more than the pre-specified non-inferiority margin of 10%. A sample size of 168 each in Arm 1 and Arm 3 achieves 80% power to detect a difference between the two proportions of less than 10%, in a one-sided test with type I error of 1.25% using

Page 7 of 25

normal approximation. Assuming no more than about 10% missing data for SPR, which includes loss to follow-up within each study arm prior to the primary outcome visit, the sample size is increased to 187 per study arm.

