2. Superiority comparison between Arms 2 and 3: For the primary objective to compare SPR proportions between Arm 2 and Arm 3 (control), an increase of 15% is assumed in the proportion of participants achieving SPR with three doses of HEPLISAV-B (Arm 2). With the sample size of 147 participants in each study arm, there is 80% power to detect a difference as significant in a two-sided test at a significance level of 2.5% using normal approximation. Formal interim efficacy analyses are planned for the Arm 2 and Arm 3 comparison, should the study enrollment allow such interim analyses to be useful to affect the conduct of the study. Assuming no more than three interim analyses for the study and applying the O'Brien and Fleming approach to preserve the two-sided type I error rate at 2.5%, Arm 2 and Arm 3 sample sizes should be at least 149 per study arm. Assuming no more than about 10% loss in the SPR data within each study arm, the targeted study sample size is 166 each for Arm 2 and Arm 3 to retain 80% power. To maintain 1:1:1 randomization across Arms 1, 2, and 3 throughout enrollment, the sample size in Arm 2 is increased to 187. Therefore, the power for the comparison between Arm 2 and Arm 3 is higher than 80%.

2.4.2 **Group B**

The study is powered to conclude that the proportion achieving SPR is greater than 55%. Assuming a response proportion of 75%, a sample size of 65 would provide at least 90% power in a two-sided test using normal approximation at a targeted significance level of 5%. Assuming at most 10% missing data, including loss to follow-up prior to the primary outcome visit, the study sample size is increased to 73.

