4.6.3 Handling of Missing Data for 4.5.1 - 4.5.5

Each analysis on antibody titers will be conducted on participants with available data, under the assumption of missing completely at random (Li, Wang, Liu, Chan, 2011).

A sensitivity analysis will be conducted for the missing HBsAb titer data at 12 weeks after the initiation of the 2-dose series and for 28 weeks after the initiation of the 3-dose series (Secondary Estimands in Sections 4.5.1, 4.5.2 and 4.5.5), with imputations analogous to what was described for SPR in Section 4.2.3 in the case that the total missing SPR results is >10%.

A sensitivity analysis will be conducted for the missing HBsAb titer data at 52 weeks after the initiation of the 2-dose series and 72 weeks after the initiation of the 3-dose series (Secondary Estimands in Sections 4.5.3 and 4.5.4), where the missing value will be imputed with the result from the subsequent visit, if there are >10% such imputations.

5 Analysis Considerations

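### The trigger for the second step of the SPR sensitivity analysis is set on total missingness, although the design allowance it refers to is about 10% within each arm

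*SAP*

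**What the plan says.** The primary SPR analysis uses participants with available data and assumes that results are missing completely at random (SAP 4.2.3). One sensitivity analysis follows, in two steps.

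- **First step, always run.** A missing SPR is filled in when the antibody results on either side of the missed visit fall on the same side of 10 mIU/mL.
- **Second step, conditional.** The condition is "If after the above imputation, the total missing SPR results is >10% (above what was accounted for in the study design". In the three-dose arms it takes a later result within 4 weeks, which admits Week 32. In the two-dose arm it takes the Week 8 result or a later unscheduled one within 4 weeks.

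The design allowance is in SAP 2.4.1. For Arm 1 against Arm 3 it reads "Assuming no more than about 10% missing data for SPR, which includes loss to follow-up within each study arm", and for Arm 2 against Arm 3 "Assuming no more than about 10% loss in the SPR data within each study arm".

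The primary SPR visit differs by arm: "at Week 12) in Arm 1 and at 4 weeks after the three-dose series (at Week 28) in Arms 2 and 3" (SAP 3.1.1).

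SAP 4.6.3 reuses the trigger for the Week 12 and Week 28 titers: "in the case that the total missing SPR results is >10" percent. Its Week 52 and Week 72 paragraph has a separate condition.

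**The concern.** The trigger refers to the design but does not test what the design allowed for. The allowance is per arm, and the test is on a total that the SAP does not define. Arm 1 reaches its primary visit 16 weeks before Arms 2 and 3, so it is likely to have fewer missing results. Adding it to the count dilutes the total.

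The first step is also not neutral between arms. In the three-dose arms, the results on either side of a missed Week 28 visit are normally those of Weeks 24 and 32. Dose 3 is given at Week 24. Secondary Objective 6 combines Arms 1 and 2 up to Week 24, which implies that the Week 24 sample precedes dose 3. Someone who first responds to dose 3 is then discordant and stays missing, while someone below 10 mIU/mL at both visits is filled in as a non-responder. In Arm 1, the neighbours of Week 12 are Weeks 8 and 24, both after its last dose. If the second step is withheld, the sensitivity analysis can therefore understate Arm 3 relative to Arm 1.

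The situation is plausible. SAP 1.2 says the extra missing-data provisions were prompted by possible pandemic losses. The Letter of Amendment (item 14, protocol 6.2.3) allows remote visits, at which a blood draw can be missed without withdrawal.

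**Working it through.** **1. The plan's own figures.** Inputs from SAP 2.4.1 are SPR of 70% and 75%, a margin of 10 points, one-sided alpha of 1.25% and power of 80%.

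n = (2.241 + 0.842)² × (0.70×0.30 + 0.75×0.25) / (0.10 + 0.05)² = 9.505 × 0.3975 / 0.0225 = 167.9, so 168.

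This agrees with "A sample size of 168 each in Arm 1 and Arm 3 achieves 80% power". The allowance gives 168 / (1 − 0.10) = 186.7, so 187, which agrees with "the sample size is increased to 187 per study arm". For Arms 2 and 3, 149 / 0.90 = 165.6, so 166, again as stated. The 10% is therefore applied arm by arm.

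**2. When each form of the trigger fires.** Because "participants are randomized in 1:1:1 ratio" (SAP 2.1.1), take 187 per arm.

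- Per arm: 10% of 187 = 18.7, so it fires at 19 missing.
- Pooled over Group A: 10% of 561 = 56.1, so it fires at 57.
- Per two-arm comparison: 10% of 374 = 37.4, so it fires at 38.

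**3. What can pass without firing.**

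| Reading of total | Arm 1 | Arm 2 | Arm 3 | Sum |
|---|---|---|---|---|
| Group A | 0 | 28 (15.0%) | 28 (15.0%) | 56 of 561 = 9.98% |
| Group A | 6 (3.2%) | 25 (13.4%) | 25 (13.4%) | 56 of 561 = 9.98% |
| Group A | 9 (4.8%) | 9 (4.8%) | 38 (20.3%) | 56 of 561 = 9.98% |
| Arm 1 against Arm 3 | 9 (4.8%) | not counted | 28 (15.0%) | 37 of 374 = 9.9% |

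**4. Dilution from visit timing alone.** Assume one constant weekly loss rate in all arms (not in the documents). When Arms 2 and 3 reach 10% at Week 28, Arm 1 at Week 12 has 1 − 0.90^(12/28) = 4.4%. The pooled figure is then (4.4 + 10 + 10)/3 = 8.1%. It reaches 10% only when Arms 2 and 3 are at 12.3% and Arm 1 is at 5.5%.

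**5. What each step does with a missed Week 28 result in a three-dose arm.**

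| Week 24 | Week 32 | After first step | After second step |
|---|---|---|---|
| <10 | <10 | non-responder | unchanged |
| ≥10 | ≥10 | responder | unchanged |
| <10 | ≥10 | missing | responder |
| ≥10 | <10 | missing | non-responder |
| any | none | missing | missing, unless another result falls within 4 weeks |

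The third row is the pattern expected of someone who responds only to dose 3.

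**6. Possible size on the SPR scale.** Assume that Arm 3 has 25 still missing after the first step, that SPR is 70% among the other 162 (113.4 responders), and that Arm 1 does not change.

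- 5 recovered as responders: 118.4 / 167 = 70.9%
- 10 recovered: 123.4 / 172 = 71.7%
- all 25 recovered: 138.4 / 187 = 74.0%

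The difference (Arm 3 minus Arm 1) rises by 0.9, 1.7 and 4.0 points. The last case is an extreme, since it allows no withdrawals.

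**7. Power.** Under the design SPRs, by normal approximation and without the interim adjustment, 6/25/25 missing gives 80.6% for non-inferiority and 84.3% for superiority. With 9/9/38, non-inferiority power is 78.3%. Lost power is not the issue.

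**The case against.** The case on the other side is strong on scope, and most of it stands.

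- **The primary result cannot move.** A reader might infer that the trigger affects the non-inferiority conclusion. It does not: both steps belong to a sensitivity analysis.
- **Withdrawal is not repaired.** A reader might infer that the second step would correct for excess withdrawal over 28 weeks. Someone who left before Week 28 has no Week 32 result. The step recovers missed draws in people who return. Step 4 of the working therefore shows only how the trigger is diluted.
- **Week 32 is not ignored.** The first step already uses it when it agrees with Week 24, and SAP 4.2.2 admits a later result when the series was delayed.
- **A gap in missingness is not a bias in SPR.** With 25 and 6 missing, the gap is 19/187 = 10.2 points, and it is tempting to set this beside the 10-point margin. The two are different quantities. In the available-case analysis, if missing participants had SPR 20 points below those observed in both arms, the net bias would be 0.102 × 20 = 2.0 points. It would raise Arm 3 and count against non-inferiority.
- **Total may mean total within each analysis.** Arm 1 then cannot dilute the Arm 2 against Arm 3 count, but it still dilutes Arm 1 against Arm 3. If total was meant within each arm, the rule already matches the design, but the text does not say so.
- **The losses remain visible.** Imputation counts by arm, numbers with data, the CONSORT diagram and discontinuation listings are all planned. None of them starts the second step.

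What is left is the mismatch between trigger and allowance, and the one-sided way in which the first step can fill in the three-dose arms.

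**Conclusion.** The point holds as a minor flaw in a sensitivity analysis. On either pooled reading, Arm 3 can be well above the per-arm allowance while the second step is not run: 13.4% with 6/25/25 missing, or 15.0% with 9 in Arm 1 and 28 in Arm 3. The sensitivity analysis can then understate SPR in the three-dose arms and look more favourable to Arm 1. The illustrated shifts are 0.9 to 4.0 points. For Arm 2 against Arm 3 both arms are affected, and the direction is not determined.

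This rests on 187 analysed per arm (the analysis set in SAP 4.2.1 may be slightly smaller), on the inference that the Week 24 sample precedes dose 3, and on some participants missing Week 28 but returning by Week 32. The documents give no expected number of such participants, so the size is illustrative. Group B has one arm and is not affected. Nothing here supports a claim that the primary conclusion is biased.

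**What to change.** In SAP 4.2.3, make one of two changes:

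1. State that the second step is applied to all arms if any arm has more than 10% of SPR results missing after the first step.
2. Remove the condition, always run the second step as an added sensitivity analysis, and report it beside the first-step result. This is simpler, and it leaves nothing to decide about the meaning of total once data from an open-label trial have been seen.

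Make the matching change in the 4.6.3 paragraph on Week 12 and Week 28 titers. The Week 52 and Week 72 paragraph has its own rule and need not change.

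The cost is one sentence in each place and one extra table, with no new data collection. One practical limit should be noted. SAP 1.1 finalizes each group's primary report after the last participant's Week 28 visit and data lock, so Week 32 results for the last participants may arrive too late. The report should state how many were unavailable for that reason.
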